Additionally, subjects must be free of serious or unstable medical illness, including renal impairment (creatinine greater than 1.4), seizures, dementia, anemia, and cannot be pregnant or nursing or have abused substances in the previous 6 weeks. Subjects with renal insufficiency are excluded because DCS is excreted unchanged in the urine; anemia is excluded because it is a rare side effect of DCS. A urine toxic screen and pregnancy test (in females) must be negative at screening. Subjects treated with clozapine will be ineligible because we and others have found that DCS worsens negative symptoms when added to clozapine (33).. Subjects treated with any SSRI will be ineligible because the PI has reviewed literature which posits that SSRI's prevent the effects of D-cycloserine on learning.

Healthy subjects will be adults between ages 18-67 with no history or current status of mental illness. In addition, healthy subjects will have normal intellectual functioning and not have any MRI contraindications.

Targeted/Planned Enrollment Table:

Ethnic Category	Sex/Gender		
	Females	Males	Total
Hispanic or Latino	2	4	6
Not Hispanic or Latino	19	35	54
Ethnic Category: Total of All Subjects *	21	39	60
Racial Category			
American Indian/Alaska Native	0	0	0
Asian	1	1	2
Native Hawaiian or Other Pacific Islander	0	0	0
Black or African American	5	11	16
White	12	30	42

Study #:S12-02991

Racial Categories: Total of All Subjects*	18	42	60
---	----	----	----

* The “Ethnic Category: Total of All Subjects” must be equal to the “Racial Categories: Total of All Subjects.”

Methods and Procedures:**Approach:**

Location: The study will be conducted at two sites. The primary site will be [name] lab within the Adult Psychiatry Clinical Trials Research space on the 8th floor of [name] and at the Bellevue Hospital Outpatient Psychiatry Department on the 2nd fl of the C & D building. Study drug will be dispensed by the NYU Research Pharmacy. Subject recruitment will occur at Bellevue Hospital. If additional subjects are required, the study will also be conducted at the Nathan Kline Institute for Psychiatric Research (NKI) which recruits subjects from the 520-bed Rockland Psychiatric Center on the NKI campus and from a network of affiliated mental health clinics. [name] is Vice Chair for Research in the Department of Psychiatry at NYU and Director of the Schizophrenia Program at NYU/Bellevue as well as Director of the NKI.

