Potential Risks: Loss of confidentiality regarding psychiatric or medical information is a possible risk for which precautions will be taken. Phlebotomy may cause soreness, bruising, bleeding and rarely, infection. A single dose of D-cycloserine 50 mg combined with CBT was well-tolerated in one cross-over study of 20 subjects exposed to drug and weekly dosing of D-cycloserine; 50 mg was well-tolerated in two studies of schizophrenia patients (n=38 subjects exposed to DCS) and in eight studies of anxiety disorder patients. However, it is possible that D-cycloserine could worsen symptoms of schizophrenia. At high doses (500-1,000 mg/d) used for the treatment of tuberculosis, D-cycloserine has been associated with confusion, lethargy, and seizures. High dose, long-term daily administration of D-cycloserine has also been associated with B12 and/or folate deficiency anemia (macrocytic anemia). It is also possible, although unlikely, that CBT will cause anxiety or agitation, insofar as it will entail participants examining their delusional beliefs.

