Protection against Risks: All patients are carefully screened to avoid enrollment of anyone for whom study procedures or study drug would be potentially harmful, including subjects with unstable medical or psychiatric illness, recent substance abuse, anemia or insufficient renal function. Subjects will be evaluated by a physician during screening and after the last dose of D-Cycloserine. A complete blood count (CBC) will additionally be performed at screening and after the last dose of D-Cycloserine. If the hemoglobin drops below 13.5 mg/100 ml for male or 12 mg/100 ml for female subjects with a mean corpuscular volume (MCV) greater than 100 (macrocytic anemia consistent with B 12 or folate deficiency), the anemia will be evaluated and treated as clinically indicated. The Side Effect Checklist for assessment of drug side effects will be administered at every visit and neurological side effect scales will be completed monthly. All information will be identified by code only. Data that are identifiable (consent forms, laboratory results, study roster and key) will be stored separately. All databases will be password-protected. Study drug will be suspended if significant clinical worsening is detected by formal assessment or clinical observation. The CBT protocol will be designed to avoid the triggering of excessive anxiety or stress. In addition, a DSMB will review the protocol prior to initiation and will monitor safety during the trial.

Justification of Potential Risks: The risks associated with this trial are minimal and the potential scientific and clinical benefits are considerable. Appropriate safeguards will be in place to ensure that the risk does not outweigh the scientific benefit.

Potential Benefits to the Subjects: All subjects will receive a comprehensive psychiatric and medical evaluation and optimal clinical treatment as part of the NYU/Bellevue Outpatient Psychiatry Department. They will also receive a CBT intervention which is not routinely available. Subjects will be closely monitored for safety. It is possible that subjects randomized to d-cycloserine may benefit with an improved clinical course, although this potential benefit has not been established by prior research.

Subject Identification, Recruitment, and Consent/Accent

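### The only numeric anemia criterion is printed in mg/100 ml; read literally, the rule for evaluating macrocytic anemia could not trigger

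*Combined protocol and SAP*

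**What the plan says.** The rule is in the combined protocol and SAP, in the Protection against Risks paragraph of the Risk/Benefit Assessment. It has two conditions and one action:

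- Hemoglobin: "If the hemoglobin drops below 13.5 mg/100 ml for male or 12 mg/100 ml for female subjects".
- Red-cell size, required at the same time: "with a mean corpuscular volume (MCV) greater than 100 (macrocytic anemia consistent with B 12 or folate deficiency".
- Action: "the anemia will be evaluated and treated as clinically indicated".

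The same paragraph says when the measurement is taken: "A complete blood count (CBC) will additionally be performed at screening and after the last dose of D-Cycloserine".

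Two other places explain why anemia is watched. The Inclusion and Exclusion Criteria say that "anemia is excluded because it is a rare side effect of DCS" and give no hemoglobin value. Potential Risks ties the risk to a different pattern of use from this trial's: "High dose, long-term daily administration of D-cycloserine has also been associated with B12 and/or folate deficiency anemia (macrocytic anemia". The Screening section lists a blood count among the routine laboratory tests, without limits.

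**The concern.** The hemoglobin limit is a decision threshold in operative safety text. Blood hemoglobin is ordinarily of the order of grams, not milligrams, per 100 ml. That is general physiology and is not stated in the documents. A limit of 13.5 or 12 mg/100 ml therefore lies far below anything a blood count could plausibly return.

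The hemoglobin and cell-size conditions must both hold, so if the first can never be true the rule can never apply. The sentence names the condition it is meant to pick up, a macrocytic anemia from B12 or folate deficiency, and as printed it could not pick it up. At stake is whether the one place that puts a number on anemia can be applied as written.

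**Working it through.** **Inputs from the protocol (Protection against Risks)**

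- Male limit: 13.5 mg/100 ml
- Female limit: 12 mg/100 ml
- Joint condition: hemoglobin below the limit and cell volume above 100

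**Input assumed**

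- Plausible blood hemoglobin of 3 to 17 g/100 ml, from severe anemia to high normal. The documents give no range.

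The limits are stated, not derived, so there is no figure of the plan's own to reproduce.

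**Step 1: convert the limits.** With 1 g = 1,000 mg, x mg/100 ml = x/1,000 g/100 ml.

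- Male: 13.5/1,000 = 0.0135 g/100 ml
- Female: 12/1,000 = 0.012 g/100 ml

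**Step 2: compare with the assumed range.** Ratio = hemoglobin in g/100 ml divided by the converted limit.

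| Assumed hemoglobin (g/100 ml) | Multiple of male limit | Multiple of female limit |
|---|---|---|
| 3 | 3/0.0135 = 222 | 3/0.012 = 250 |
| 17 | 17/0.0135 = 1,259 | 17/0.012 = 1,417 |

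Every value in the range lies above both limits. A different range changes the multiples but not the result: 5 to 20 g/100 ml gives 370 to 1,481 times the male limit (5/0.0135 and 20/0.0135).

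**Step 3: apply the joint condition.** If hemoglobin is never below the limit, the conjunction with cell volume is never true, whatever the cell volume is.

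**Step 4: look for a repair elsewhere.** The eligibility criteria exclude anemia without a number, Screening lists the blood count without limits, and Potential Risks describes the anemia in words only. None gives a hemoglobin value or unit, so the intended unit cannot be recovered from another section.

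**Step 5: consider a text-extraction fault.** The unit appears twice in the sentence, once per sex and in the same form, and the sentence is otherwise intact. A reading artefact is unlikely.

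**The case against.** The strongest reply is that this is a typographical slip that would mislead nobody in practice. A physician evaluates each subject after the last dose, when the second blood count is taken. A clinician comparing that report with the protocol would probably see that the unit is wrong, and the sentence itself says what kind of anemia is meant. The error is also shown only by outside physiology; no two figures in the documents disagree. These points stand, and they keep the severity low. They do not make the sentence right: it works only if the reader disregards the unit it prints.

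Three stronger readings are tempting, and the documents do not support them.

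- *The trial has no working anemia safeguard.* Subjects with anemia are excluded, blood counts are taken at screening and after the last dose, a physician evaluates subjects at both points, a side-effect checklist is completed at every visit, and a safety board monitors the trial. None of these depends on the unit. The sentence is the only numeric anemia criterion, not the only safeguard.
- *A programmed check would silently miss cases.* Data Management and Quality Assurance describes staff review for accuracy, completeness and logical consistency. It mentions no electronic hemoglobin check.
- *Treatment or results are affected.* The action is clinical evaluation. The only blood count specified after screening follows the last dose, and no stopping rule, endpoint, power figure or analysis uses the limit. Potential Risks associates the anemia with high-dose, long-term daily use, whereas this trial gives 50 mg before weekly sessions, and the eligibility text calls it rare.

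The multiples in the working should not be taken as bounds on every value that could be observed, since they follow from an assumed range. What the documents and arithmetic fix is the conversion by 1,000.

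**Conclusion.** The criterion is wrong as written. Its literal limits are 0.0135 and 0.012 g/100 ml. On any plausible hemoglobin range the joint condition could not be met, and the sentence would defeat its stated purpose. The conversion is exact. The only assumption is that blood hemoglobin lies in grams per 100 ml; with a floor of 3 g/100 ml the margin is at least 222-fold.

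The practical effect is limited. It is probably a unit slip, the other anemia safeguards are independent of it, and neither the efficacy inference nor any stopping rule is touched. It merits a low-severity correction. Whether the numerals are the intended ones in some other unit is for the sponsor to confirm; the documents do not settle it.

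**What to change.** The sponsor's clinicians should check the unit in Protection against Risks against the unit in which the laboratory reports hemoglobin, confirm the intended male and female values, and correct both occurrences in the sentence. Any document derived from that text should be corrected to match. No threshold value is proposed here.

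The cost is a wording correction in one sentence, with no change to design, sample size, visit schedule or analysis.
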